**Exclusion Criteria:**

- 1) Thrombocytopenia or other bleeding disorders;
- 2) Patients on anticoagulation therapy with an INR > 3.5;
- 3) Severe or anaphylactoid reactions to IVIG;
- 4) Cancer (active or currently treated);
- 5) Pregnancy;
- 6) Breast-feeding;
- 7) Renal insufficiency (creatinine > 1.5 upper limit of normal) or failure;
- 8) Congestive heart failure;
- 9) Psychiatric illness that would interfere with ability to provide informed consent or adhere to protocol;
- 10) Current IVIG doses greater than 2 g/kg per month;
- 11) Subject with an IgA level < 5% lower limit of normal;
- 12) History of active infection with HIV, Hepatitis B or Hepatitis C;
- 13) Presence of any other medical condition, which in the opinion of the investigator might interfere with performance;
- 14) Participation in a trial of an investigational medicinal product for CIDP in the past 12 weeks.

**Sample size and statistical analysis:** Descriptive information for the rate of change, such as mean and standard deviation, will be calculated. Due to the small sample size and self-control used in this study, instead of using paired t-test, Wilcoxon paired ranked test will be used to compare the change of before and after from each patient. Significance level is defined as 0.05 and all of the analyses will be carried by SAS (version 9.2).

**DESIGN:** The study will be submitted to the USF IRB for approval.

**Specific Aim #1.** We will assess QOL using the Medical Outcome Study 36-item short form health status scale (SF-36) and the Rasch-built Overall Disability Scale (R-ODS). The scales have been validated in patients with CIDP (Merkies et al, 2002; van Nes et al, 2011). We will also do a survey of side effects and satisfaction with treatment (using the Treatment Satisfaction Questionnaire for Medication, or TSQM) and CIP-PRO20 scale (used by permission from [name]; see appendix 3). No surveys will be completed until the patient signs the ICF. In addition, we will determine whether patients currently treated with IVIG would be willing to try the SC route of administration. Reasons cited for unwillingness to switch will be collected.

Specific Aim #2. To test the safety and tolerability of SCIG and feasibility of self-administration in patients with CIDP.

Patients will undergo baseline laboratory studies (CBC, CMP, TSH, quantitative IgG, PT/INR/PTT, pregnancy test for women of productive age), EKG, QOL questionnaires, treatment satisfaction and SE questionnaires, neurological and physical examination, and HHD measurements.

The study will provide all study medications, pumps, and supplies.

The first treatment of SCIG will start within 2 weeks after the last IVIG course (to maintain serum Ig levels). The first 2 weekly treatments will be done at USF Clinical Research Center (USF CRC). Patients will be trained to perform their own infusions during these initial sessions and will receive additional training sessions if needed. Subjects will start self-administration at home after they feel comfortable and confident with the procedure. For each weekly treatment, 20% solution of human normal IgG (Hizentra, CSL Behring AG) will be infused subcutaneously in the abdomen, flanks, arms, or thighs. Simultaneous SC infusion at multiple sites will be done using a multi-needle administration set. The volume at each infusion site will be 35 ml (7 g) or as tolerated, and administered via a syringe driver pump at a rate of 20-25 ml/hr/site or as tolerated. For this study, we will use a 1:1 conversion ratio for IV to SC dosing. The total SC dose weekly will be the patient's current IVIG dose divided by 4 (0.25 g/kg – 0.5 g/kg, corresponding to 1 – 2 g/kg per month, which is usually our maintenance dose for CIDP patients). Patients requiring > 2 g/kg of IVIG per month will be excluded from study. Weekly doses may be divided over the course of the week if needed (e.g., twice or three times a week). The SCIG will be given weekly for 24 weeks. The dosing will be individualized to each patient depending on dose and patient response. The regimen may be changed at any point as needed for patient comfort (e.g., a patient may increase his/her dosing schedule from 1 day to 2 or 3 days per week). After this period, the patients will be given a choice to discontinue treatment, continue with SCIG, or go back to IVIG. Pregnancy screen will be performed monthly on women with reproductive potential while they are undergoing treatment. If a subject becomes pregnant during the study, she will be withdrawn from treatment but will be monitored for the rest of the study. Please see table 2 for schedule of study visits. Study subjects will be monitored for allergic reactions (rash, urticaria, facial edema, wheezing, dyspnea, hypotension, and tachycardia) and injection site reactions (transient swelling, soreness, redness, induration, local heat, and itching) while receiving their first infusion at USF CRC. They will also keep a treatment log of injection site reactions for the duration of the study.

Additional monitoring includes:

1. CBC with differential count and platelet count will be done prior to treatment and once per month during treatment.
2. Symptom monitoring will be done via phone and at scheduled visits at regular intervals. Study visits will have a window of +/- 7 days. Patients will have 24/7 access to investigators to report any symptoms that develop.
3. Subjects will be provided with emergency contact number for questions relating to any symptoms during the study.
4. In the event that the subject experiences a reaction at home, they will call us. They will also be trained to call 911 in an emergency situation.

Primary End-Points.

1. Significant side-effects requiring withdrawal from study.
2. Laboratory abnormalities requiring discontinuation of study.

**Table 2.** Schedule of Study Events and Visits.

	Screening	Day 1	Week 1	Week 2*	Week 3*	Week 4 (Month 1)	Week 8 (Month 2)	Week 12 (Month 3)	Week 16 (Month 4)	Week 20 (Month 5)	Week 24 EOS/ET (Month 6)	Follow-Up
	V1	V2	V3	V4	V5	V6	V7	V8	V9	V10	V11	V12
Informed Consent	x											
Inclusion/Exclusion Review	x	x										
Medical History	x	x	x									
Vital Signs Monitoring	x	x	x	x	x	x	x	x	x	x	x	
Physical/Neuro Exam	x	x	x			x	x	x	x	x	x	x
TSQM	x	x	x			x	x	x	x	x	x	
CIP-PRO20	x	x	x			x	x	x	x	x	x	
R-ODS	x	x	x			x	x	x	x	x	x	
SF-36	x	x	x			x	x	x	x	x	x	
Hand-held Dynamometry	x	x	x			x	x	x	x	x	x	
20-ft Timed Walk	x	x	x			x	x	x	x	x	x	
Electrocardiogram (ECG)	x											
PT/INR, PTT	x											
TSH	x											
Quantitative IgA, IgG, IgM	x	x				x	x	x	x	x	x	
Hematology, blood chemistry	x		x			x	x	x	x	x	x	x
Urine Pregnancy Test	x	x	x			x	x	x	x	x	x	
Subcutaneous Drug Administration Training	x	x	x	x								
Subcutaneous Drug Administration	x	x	x	x								
Drug Diary Training	x	x										
Drug Diary Review				x	x	x	x	x	x	x	x	
Drug Dispensation	x	x	x	x	x	x	x	x	x	x	x	
Drug Accountability							x	x	x	x	x	

\* optional for additional administration training (can be completed at home)

Specific Aim #3. To test the hypothesis SCIG is associated with better QOL.

At baseline (pretreatment of SCIG, while subjects are being treated with IVIG), QOL and treatment satisfaction questionnaires (SF-36, CIP-PRO20, R-ODS, and TSQM) will be done. These measures will be repeated monthly during the course of the study. Data from pretreatment and treatment with SCIG phase will be compared using appropriate statistical methods with correction for multiple comparisons.

Specific Aim #4. To test the hypothesis that SCIG is efficacious in controlling the symptoms of CIDP.

Clinical response to SCIG will be monitored using HHD and 20-ft timed walk. Data from pretreatment and SCIG treatment phase will be compared. The HHD will measure force generated by the following muscle groups: Shoulder flexion, elbow flexion, elbow extension, wrist extension, first dorsal interosseous (hand), hip flexion, knee extension, knee flexion, ankle dorsiflexion. Measurement will be done bilaterally in duplicates. For the primary efficacy endpoint, HHD muscle strength measured at Week 24 will be compared to HHD muscle strength measured at baseline (pretreatment)

Secondary End-Point.

1. Progression of symptoms requiring reversion to IVIG, initiation of PLEX or other medications, or hospitalization.

**Study Timeline and Feasibility:** Participants will be recruited from the USF Neuromuscular Clinic. This Clinic is the tertiary referral center for the west coast of Florida, with a population of more than 4 million in the Tampa Bay region alone. We estimated that we have more than 70 patients with CIDP. In addition, we see an average of 2 new CIDP patients per month. Thus, there are enough patients for a 3 to 1 screening to enrollment ratio. Planned recruitment is an average of 1 patient every 1.5 months, for a total of 22.5 months. This schedule will place the final recruit completing the trial during month 30 and afford time during the final 6 months of the study for analyzing and preparing data for publication. This planned recruitment timeline is feasible given the size, established referral patterns, and historical recruitment experience of this clinic.

**Rescue protocol:** If a subject worsens (or “relapses”) during the study, we will institute a rescue protocol. Relapse is defined as a 20% decrease in force (as detected on HHD) in more than 50% of the muscles tested when compared to baseline. In case of relapse, we will quantify the serum Ig levels, give IVIG 1 g/kg boost followed by SCIG at 2 g/kg per month. If the subject is already on 2 g/kg per month of SCIG, we will switch the patients back to IV administration and/or institute other treatment options (steroids, PLEX). Please see algorithm in Appendix 2. We will also switch back to IVIG if, at any point during the study:

- a. The subject requests the switch due to treatment failure, adverse events or patient preference.
- b. The investigators consider it to be in the best interest of the subject (i.e., due to intolerable side-effects, pregnancy, or noncompliance).

**Potential Pitfalls and Alternative Strategies:** There is the potential that some patients may lose interest or become too reticent in performing self-administration. Since compliance may be an issue with self-administration of an injectable medication, serum IgG levels will be done to monitor patient’s adherence to protocol. The use of a home journal for recording therapy and a weekly telephone call will encourage compliance. In the scenario where there is concern with patient compliance, a weekly home therapy visit will be done. Attrition is also expected during the course of the study. If a participant becomes a ‘drop out,’ his or her data will be used in the analysis using an intention to treat protocol. Finally, while recruitment can be an issue in clinical trials, our planned enrollment rate of an average of 1 patient per 1.5 months is feasible. Furthermore, we already identified several patients who are appropriate for this trial. With an average of 2 new CIDP patients seen per month in the USF Neuromuscular Clinic, we should be able to recruit the remaining patients in the proposed timeline. Furthermore, there are many more CIDP patients in the greater Tampa region who are not being seen at USF. Thus, there is an untapped pool of subjects available. In the unanticipated scenario that we fall behind on subject recruitment, we have incorporated 6 additional months in our timeline for analysis and manuscript preparation that could be utilized for subject recruitment and treatment.

**Data Management and Quality Control:** Physiologic and questionnaire data will be collected across two time points (pre- and SCIG treatment phase) by the PI and coordinator who are all proficient in these testing methods. To ensure participant confidentiality, data will be coded to remove patient identifiers into a password-protected database (Excel) on a central computer system that is backed up daily. Data accuracy will be verified by double data entry. All original paper questionnaires will be locked in the PI’s office with only coded identifying information. There will be an interim analysis done after 8 patients have completed the study.

**Safety Monitoring and Adverse Events Reporting:** Patients will be closely monitored for safety and any adverse events. This monitoring of treatment tolerability will be achieved through weekly telephone contact and monthly visit. During the study visits, subjects will be seen by a member of the research staff and will complete all study instruments, undergo clinical assessment, and have blood drawn for safety and compliance monitoring. At all study visits, concomitant medications, symptoms and side effects will be reviewed. Participants will also be provided with the Study Agent Intake and Symptom log which they will be required to complete. Adverse

Events will be reported to sponsor, USF IRB and regulatory agency, by investigators in a timely manner as required.

Dose and Toxicity Management:

A patient's treatment will be suspended in any of the following circumstances:

1. Allergic reaction to product
2. Request of patient or patient's physician;
3. Unusual symptoms reported during telephone follow-up or other unusual symptoms or blood work results observed during the study period
4. Pregnancy; or
5. Worsening symptoms requiring hospitalization or PLEX.

Any side effects associated or possibly associated with SCIG will be managed according to standard medical practice.

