
## SPECIFIC AIMS

As of October 2012, we identified more than 70 patients with the diagnosis of CIDP at the University of South Florida (USF) Neurology Clinic. We estimated that at least 2/3 of these patients meet the Inflammatory Neuropathy Cause and Treatment (INCAT) Group diagnostic criteria (Sander & Latov, 2003). Many of these patients still attend our clinic and many are dependent on IVIG to control symptoms. Data are lacking in terms of tolerability, although our physicians are often contacted by patients or infusion centers for guidance regarding treatment of Ig infusion related side effects such as hypertension, flu-like symptoms, headaches, and joint pain.

Specific Aim #1. This study will assess the QOL and adverse events experienced by patients on IVIG and whether patients currently treated with IVIG would be willing to try the SC route of administration. This specific aim will be achieved via telephone or face-to-face survey. The goal is to identify factors that may reduce the patients' willingness to consider alternate drug delivery method.

Specific Aim #2. For patients willing to switch to SCIG, this study will test the hypothesis that SCIG is safe and well tolerated and can be self-administered by patients with CIDP. We will monitor patients' adverse reactions via patient diary, questionnaires, examination, and laboratory studies.

Specific Aim #3. To test the hypothesis that SCIG is associated with better QOL, we will compare QOL measures pre- and post-treatment.

Specific Aim #4. We will collect clinical data to test the hypothesis that SCIG is efficacious in controlling the symptoms of CIDP. Patients will be followed with hand-held dynamometry (HHD) and 20-ft timed walk. Pre- and post-treatment scores will be compared using appropriate statistical analysis.

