### **APPROACH:**

This is a prospective, open label study of SCIG for the treatment of patients with CIDP who are dependent on IVIG for control of symptoms.

**Participants:** Up to 30 patients with IVIG-dependent CIDP will be enrolled. To qualify, a patient must meet **ALL** of the inclusion criteria and **NONE** of the exclusion criteria.

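### Do the Aim 2 primary endpoints miss patients who stop SCIG for side effects but stay in follow-up?

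*Combined protocol and SAP*

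**What the plan says.** Under Specific Aims, the protocol states for Aim 2 that "this study will test the hypothesis that SCIG is safe and well tolerated and can be self-administered by patients with CIDP". Under Specific Aim #2, Primary End-Points, it lists two events: "Significant side-effects requiring withdrawal from study" and "Laboratory abnormalities requiring discontinuation of study".

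The secondary endpoint, under Specific Aim #4, is "Progression of symptoms requiring reversion to IVIG, initiation of PLEX or other medications, or hospitalization". Return to IVIG therefore counts there when progression is the cause.

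The Rescue protocol lets a patient go back to IVIG at any time. This may be at the patient's request, with adverse events among the reasons, or by investigator decision, with intolerable side effects among the reasons. Dose and Toxicity Management lists reasons for suspending treatment, including allergic reaction and blood results. None of these rules says whether the patient also leaves the study. The Rescue protocol adds "Please see algorithm in Appendix 2". The algorithm is not reproduced in the text available here, so its content is unknown.

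For pregnancy alone, the treatment description under Specific Aim #2 separates the two states: "she will be withdrawn from treatment but will be monitored for the rest of the study".

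On size, the Approach section says "Up to 30 patients with IVIG-dependent CIDP will be enrolled".

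**The concern.** Stopping a drug and leaving a trial are different events, and a tolerability endpoint should follow the first. The endpoint wording follows the second. The pregnancy rule shows that this protocol can keep a patient under observation after treatment ends. Pregnancy also appears beside intolerable side effects as a reason for the same investigator-led switch to IVIG, so a switch does not automatically mean withdrawal.

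If patients switched for side effects also stay, the word-for-word endpoint would omit the very patients it is meant to find. The secondary endpoint would not recover them, because it requires symptom progression. The primary tolerability rate would be too low, and two analysts could report different rates from the same data.

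**Working it through.** The documents give no expected rate, threshold or power for the Aim 2 endpoints, so there is no figure to reproduce. The check has three steps.

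**1. When is an event lost?** Take a patient switched to IVIG for a significant side effect, with no symptom progression. Two things are open: whether the patient stays in follow-up, and what *study* means in the endpoint.

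| After the switch | *Study* read literally | *Study* read as study treatment |
|---|---|---|
| Patient leaves the study | Counted in primary endpoint 1 | Counted in primary endpoint 1 |
| Patient stays in follow-up | Counted in no endpoint | Counted in primary endpoint 1 |

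Only one of the four cells loses the event. It needs both conditions together; continued follow-up alone is not enough. The same table applies to laboratory abnormalities and primary endpoint 2.

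**2. Which cell does the text support?**

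- The endpoints speak of events that *require* withdrawal or discontinuation. A side effect or laboratory value can require that a drug be stopped. It hardly requires that observation end.
- Both endpoints sit under the aim on the safety and tolerability of SCIG. The description of what happens after 24 weeks also uses the verb *discontinue* for treatment.
- The Week 24 column of Table 2 is headed "Week 24 EOS/ET (Month 6"), so one visit serves as end of study and early termination. Data Management and Quality Control describes data collection for only two phases, before SCIG and on SCIG. Both fit a design in which a patient who stops SCIG has an exit visit and is finished.
- The pregnancy sentence can be read either way. It shows that treatment and study status can differ. Since it adds continued monitoring for one reason only, it can also be read as an exception to a general rule that stopping treatment ends participation.

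The text favours cells in which the event is counted, though it does not exclude the fourth.

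**3. How large could the error be?** Inputs: n = 30, the enrolment maximum; x = number of counted events, assumed because the documents give none. The rate is x/n. The exact (Clopper-Pearson) 95% limits are the 2.5% quantile of Beta(x, n − x + 1) and the 97.5% quantile of Beta(x + 1, n − x). For x = 0 the lower limit is 0 and the upper is 1 − 0.025^(1/n), which at n = 30 is 11.6%.

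Assume 3 of 30 patients stop SCIG for side effects and *study* is read literally:

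| Of the 3, number who stay in follow-up | Counted | Rate | Exact 95% CI |
|---|---|---|---|
| 0 | 3/30 | 10.0% | 2.1–26.5% |
| 1 | 2/30 | 6.7% | 0.8–22.1% |
| 2 | 1/30 | 3.3% | 0.1–17.2% |
| 3 | 0/30 | 0% | 0–11.6% |

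Each patient counted differently moves the rate by 1/30 = 3.3 percentage points at full enrolment, and by more with fewer patients. The recruitment schedule in Study Timeline and Feasibility, one patient per 1.5 months for 22.5 months, gives 22.5/1.5 = 15 patients. The step is then 1/15 = 6.7 points, and 3/15 = 20.0% (4.3–48.1%) could fall to 0/15 = 0% (0–21.8%). If *study* means study treatment, every shift is zero.

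**The case for a change.** The strongest case for acting is that a primary endpoint should not rest on inference. The protocol writes of withdrawal from treatment where it means treatment, in the pregnancy sentence, and of withdrawal from study in the endpoint, so the contrast could be deliberate. The combined end-of-study and early-termination visit comes with no stated trigger. The intention-to-treat sentence under Potential Pitfalls says that drop-outs' data are used, but not whether a switched patient is a drop-out. With 15 to 30 patients, one reclassified case is visible in the result, and clarifying wording would cost little.

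The ambiguity stands: the visible text does not settle follow-up after a switch for side effects. What does not stand is the step from ambiguity to a wrong count. The plan contains no rule that makes an analyst drop such a patient, and someone summarising SCIG tolerability would naturally count side effects that ended SCIG. Appendix 2 may also bear on the point, although its title concerns relapse. Its absence from the extracted text cannot be held against the plan.

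The obvious rewording has a cost of its own. Defining the event as any permanent stop of SCIG because of a side effect would drop the conditions that the effect be significant and that it require stopping. A switch requested for a minor adverse event would then count, which changes the endpoint rather than clarifying it. A stated denominator, exact intervals and a coded reason for stopping are reasonable reporting choices, but they do not correct an error.

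**Conclusion.** The concern does not call for a change. The endpoint wording is loose, but its natural meaning in an SCIG tolerability aim is a significant side effect, or a laboratory abnormality, that requires study treatment to be stopped. On that meaning the effect is zero whether or not patients stay in follow-up.

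A loss would need a patient switched for side effects who stays in follow-up, has no symptom progression, and is classified by a strictly literal reading. The documents do not show that this would happen, and the size cannot be derived from them. As an assumed illustration, 3 lost events in 30 would turn 10.0% into 0%.

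Even then the consequence is limited. This is an open-label pilot with no threshold or decision rule attached to these endpoints. The events would still appear in the adverse event data gathered through the symptom log, weekly calls and monthly visits. This conclusion assumes that the analysts apply the treatment-based reading consistently when they classify stops.

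### No hematology or chemistry sample is scheduled on Day 1, so a laboratory abnormality first seen at Week 1 may not be datable to before or after the first SCIG dose

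*Combined protocol and SAP*

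**What the plan says.** In the combined protocol and SAP, the row "Hematology, blood chemistry" of Table 2 is marked at Screening, Week 1, Weeks 4 to 24 and Follow-Up. Its Day 1 cell is empty. The row "Quantitative IgA, IgG, IgM" is marked at both Screening and Day 1, so blood is taken on Day 1 anyway.

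The text does not fill the gap. The monitoring list under Specific Aim #2 says "CBC with differential count and platelet count will be done prior to treatment and once per month during treatment", which the Screening sample satisfies. The baseline laboratory list in the same section includes CBC and CMP but names no visit.

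On timing, Specific Aim #2 states: "The first treatment of SCIG will start within 2 weeks after the last IVIG course". Specific Aim #3, describing when the questionnaires are first given, places baseline in the IVIG period: "At baseline (pretreatment of SCIG, while subjects are being treated with IVIG". The only visit tolerance stated is plus or minus 7 days. No longest permitted interval between Screening and Day 1 appears.

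The second primary end-point is "Laboratory abnormalities requiring discontinuation of study". It has no attribution condition and no defined laboratory reference. The list of reasons for suspending treatment, under Dose and Toxicity Management, includes unusual blood results in the study period, also without an attribution condition.

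**The concern.** The study is open label with one arm. It moves patients directly from IVIG to SCIG and makes laboratory-driven discontinuation a primary safety end-point. With no concurrent IVIG group, only the order of events within each patient can show whether an abnormality preceded SCIG. That requires a sample taken just before the first SCIG dose.

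As scheduled, the last look before SCIG is at Screening and the next is at Week 1. If an IVIG course ends in between, an abnormality that is absent at Screening and present at Week 1 has two candidate sources and no sample that separates them. The Background lists renal failure among the side effects of IVIG, so at least one relevant abnormality would be visible on a chemistry panel. A pre-dose sample that was never drawn cannot be recovered later.

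**Working it through.** The plan gives no sample-size, power or event-rate figure for this end-point, so there is nothing to reproduce. The check covers the table, the timing rules and the size of one event.

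**1. Is the blank cell real?** Table 2 has 12 visit columns. The hematology and chemistry row has 12 cells: marks at V1, V3 and V6 to V12, blanks at V2, V4 and V5. Its last mark is in the last column, so the row cannot have slipped sideways. The immunoglobulin row also has 12 cells, with marks at V1, V2 and V6 to V11. The blank on Day 1 (V2) is real, and so is the Day 1 blood draw.

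**2. Can an IVIG course end after the Screening panel?** Let G be the days from Screening to Day 1 and T the days from the end of the last IVIG course to Day 1. The two-week rule gives 0 ≤ T ≤ 14. G has no stated limit. The course ends after the Screening sample when T < G.

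- If G > 14, then T ≤ 14 < G, so it always does.
- If G ≤ 14, it may. Assuming T is uniform on 0 to 14 days (the documents give no distribution), the probability is G/14: 3/14 = 21%, 7/14 = 50%, 10/14 = 71%, 14/14 = 100%.

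The same rule gives a lower bound that does not need G. A patient screened more than 14 days after a course cannot start SCIG without another one. Assuming Screening falls uniformly over an IVIG cycle of C days, the share affected is at least (C − 14)/C. The documents do not state C. The share is 7/21 = 33% for C = 21, 14/28 = 50% for C = 28, 28/42 = 67% for C = 42, and zero for C = 14.

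**3. What does the Week 1 panel follow?** At nominal timing it falls T + 7 days after the last IVIG course, that is 7 to 21 days, or up to 28 with the +7-day window. By then the patient has had one weekly SCIG dose, or two if blood is drawn after the Week 1 infusion (the order is not stated). Each is a quarter of the current IVIG dose. Recent IVIG exposure is therefore at least as plausible a source as SCIG.

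**4. How large is one event?** N is up to 30 (Participants). The recruitment plan under Study Timeline and Feasibility implies 22.5/1.5 = 15. Exact (Clopper-Pearson) 95% intervals:

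| N | No event | One event |
|---|---|---|
| 30 | 0% (0 to 11.6) | 1/30 = 3.3% (0.1 to 17.2) |
| 15 | 0% (0 to 21.8) | 1/15 = 6.7% (0.2 to 31.9) |

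These figures show what one discontinuation is worth. They do not estimate how often one would be wrongly attributed.

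**5. What would a pre-infusion Day 1 panel change?** The interval between the last reference panel and the first SCIG dose falls from G days to zero, and no IVIG course can end inside it. An abnormality already present on Day 1 is then known to precede SCIG. One absent on Day 1 and present later arose after the switch, although a late IVIG effect remains possible.

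**The case against.** **The end-point uses no baseline.** It counts discontinuations, so a Day 1 sample alone changes no count. This is correct. A reader might infer that the schedule biases the primary result, or that IVIG effects are charged to SCIG. The documents do not support that: no text assigns causality, and no change from a laboratory baseline is analysed for this end-point. What stands is narrower: such an event would be counted, and the data could not show when it began.

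**Screening is itself an on-IVIG sample.** Patients depend on IVIG, so abnormalities that persist or recur with it can already show at Screening. Only a new abnormality from the final course would be missed, and it must be serious enough to stop the study. This reduces the expected number. The Background puts systemic IVIG side effects at about 5%, or 0.75 patients of 15 and 1.5 of 30, but that covers all the listed effects, mostly symptoms. It cannot be turned into a rate for this end-point.

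**Other text may cover Day 1.** Safety Monitoring says blood is drawn at study visits for safety and compliance. That sentence follows a reference to the monthly visit and names no test, so it does not override an empty cell in the schedule.

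**The table is unclear about when SCIG starts.** As printed, the Subcutaneous Drug Administration row is also marked at Screening. Read literally, the first dose could fall on the day of the Screening draw and the gap would vanish. That conflicts with a separate Day 1 at which eligibility is still being reviewed. The entries must be reconciled, but they do not rescue the schedule.

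**Eligibility.** A reader might also infer that patients who no longer meet "Renal insufficiency (creatinine > 1.5 upper limit of normal) or failure" or the thrombocytopenia exclusion will start SCIG unnoticed. The Day 1 review indeed has no fresh panel, but the documents do not say that it must re-test laboratory criteria, and nothing shows that such patients would occur. The point does not rest on this.

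**Conclusion.** The point holds as a gap in attribution and is worth correcting because the remedy is cheap. The only scheduled pre-SCIG hematology and chemistry panel can predate the end of the last IVIG course, and must do so when Screening is more than 14 days before Day 1. In those patients an abnormality first seen at Week 1 cannot be dated relative to the first SCIG dose, and a single-arm design offers no other means of separating the causes.

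The conclusion rests on Table 2 as printed, the two-week rule, IVIG continuing through baseline, and the absence of a limit on the Screening-to-Day 1 interval. The probabilities for shorter intervals and the shares by cycle length depend on the uniform-timing assumptions stated with them. One event would be 3.3% of 30 patients or 6.7% of 15. It would be wrong to read those percentages as the expected bias, because the documents give no rate for laboratory-driven discontinuation.

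**What to change.** - Mark "Hematology, blood chemistry" at Day 1 (V2) in Table 2, drawn before the first infusion from the venipuncture already scheduled for immunoglobulins.
- Define that sample in the text as the laboratory reference for Primary End-Point 2.
- Report Primary End-Point 2 in two ways: all discontinuations for laboratory abnormality, and the same events split by whether the abnormality was already present on Day 1. Without this split the extra sample would not affect the report.
- Reconcile the Screening mark in the Subcutaneous Drug Administration row with the existence of a separate Day 1.

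The cost is one additional CBC and chemistry panel per patient, 15 to 30 in total, with no additional visit or needle stick. IVIG effects that first appear after Day 1 would still not be separated from SCIG effects, and the report should say so. No eligibility criterion or clinical threshold changes.
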